Research hypothesis

Ho: The change in the score of the IIEF-EF scale in patients with moderate erectile dysfunction³, treated with radial wave therapy, is equal to those who receive placebo therapy.

Ha: The change in the score of the IIEF-EF scale increases at least five points in patients with moderate erectile dysfunction treated with radial wave therapy, compared with the score of patients receiving placebo therapy.

Study population

Patients diagnosed with erectile dysfunction of vascular origin who are treated at the Boston Medical Group facilities in Bogotá.

Inclusion criteria

- 1. Men older than 18 years
- 2. Erectile dysfunction presents for more than 3 months in more than 50% of intercourse.
- 3. IIEF-EF score between 11 and 21.
- 4. Patient who agrees to enter the study through the signing of an informed consent.

Exclusion criteria

- 1. EHS score of 4
- 2. Bladder, prostate or colon cancer.
- 3. Patients with ED of psychological origin.
- 4. Patients with spinal cord injury.
- 5. Patients with anticoagulant use.
- 6. Patients with sickle cell anemia.
- 7. Patients with clinical suspicion of hypogonadism (AMS greater than 36, Annex 1).
- 8. Patients with infections or active lesions of the penis or pubic area.
- 9. Patients with ED secondary to drug treatment (antiandrogenic therapy, antidepressants, use of corticosteroids, antiparkinsonians, antipsychotics).
- 10. Radical prostatectomy or other radical pelvic surgery.
- 11. Antecedents of pelvic radiotherapy.
- 12. Patients with penile implant.
- 13. Endocrine diseases that occur with ED: acromegaly, gigantism, Addison's disease, hyperprolactinemia, androgenic deficiency.
- 14. Patients with neurological diseases (Parkinson's, CVD, dementia of any origin)

³ For this study moderate erectile dysfunction is considered a score on the IIEF-EF scale from 11 to 21, which includes the mild to moderate and moderate categories.

Sample size

Assuming that the placebo plus drug group has an average change in the score of the IFE-EF scale of 5 points and that the new wave therapy must have an additional change of at least 5 points to be considered clinically relevant, for a power of 80% and a one-tailed level of significance of 97.5%, with a standard deviation of 8 points, a sample size of 33 patients was estimated for each group. Adjusting for a percentage of losses of 20%, the size per group is 40 patients, for a total of 80 patients in the study. These calculations were performed in Stata 15.1®.

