Interventions

Each patient will be assigned randomly to one of the following groups:

- Arm 1 (Radial wave therapy + oral treatment): 6 radial waves' sessions. A weekly session of radial waves will be applied with the following parameters: 6000 pulses at 1.5-2.6 bar (depending on patient tolerance), with a frequency of 17Hz, the frequency should increase to 22HZ the first 500 impulses to create mild anesthesia in the area; in all the sessions of radial waves, 4000 impulses will be distributed in the body of the penis in scanning technique and 2000 impulses in the perineal area, specifically in the ischiocavernosus and bilateral bulbo-sponge muscles. During the period of therapy application, patients will receive oral treatment with sildenafil 4 according to the patient's degree of affectation.
- Arm 2 (Placebo therapy + oral treatment): 6 sessions of placebo therapy. There will be a weekly session of placebo wave therapy, using the respective device to prevent the patient from receiving the radial wave. The same parameters of the "real" therapy will be used: 6000 pulses at 2.6 bar, with a frequency of 17 Hz; in all the sessions of radial waves, 4000 impulses will be distributed in the body of the penis in scanning technique and 2000 impulses in the perineal area. During the period of therapy application, patients will receive oral treatment with sildenafil 5 according to the patient's degree of affectation.

The radial waves will be administered with the Masterpuls MP50 device from Storz medical.

Primary Outcome

The primary outcome of this study is the difference in the average score of the IIEF-EF scale (Annex 3) in at least 5 points at the end of the treatment.

Secondary outcomes

- IIEF-EF score after one month of follow-up.
- Erection Hardness Score (EHS) at the end of treatment and one month follow-up: The EHS is a unique Likert scale and the version validated in Spanish (35) will be used, which has the following score, 0: The penis does not change in size or hardness; 1: The penis increases in size but does

⁴ This is the standard treatment.

⁵ This is the standard treatment

not become rigid; 2: The penis is rigid but not enough to penetrate; 3: The penis is rigid enough for penetration but not completely hard; and 4: The penis is completely hard or rigid (Annex 4).

- Change in the dose or use of sildenafil.
- Incidence of adverse events.

Safety

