It will be determined by the presence of adverse events. These will be evaluated at the end of each of the therapies and a month of follow-up. This variable will be dichotomous as the presence or absence of adverse events. Additionally the type of adverse event and the degree of severity will be recorded.

Randomization

The assignment of patients to the treatment arms will be done with the method of randomization by balanced blocks of unequal cells. The assignment of the treatment will be centralized, so once the patient agrees to participate in the study and signs the informed consent, an email should be sent to the research center ([contact]) who will only inform the therapist which is the group (intervention or control) that corresponds to the patient.

To conceal the assignment sealed opaque envelopes will be used, this envelope will be opened once the request is generated in each center, after the patient has voluntarily accepted to participate in the study and the informed consent process has been carried out with signature of the written document.

Neither the patient, the attending physician, nor the professional who applies the questionnaires will know the group to which the patient was assigned.

Techniques, procedures, data collection and processing

The subjects who attend consultation for erectile dysfunction at the Boston Medical Group clinics in Bogotá (Colombia) and Lima (Peru), will be treated as usual according to the institutional management protocols and screened to determine if they meet the eligibility criteria. If so, they will be invited to participate in the research project and the informed consent process will be carried out in which the objectives, risks, benefits, procedures and other relevant research data will be explained.

Once the patient has voluntarily accepted to participate in the study and the informed consent document has been signed, an email will be generated to the research center to request the group to which the patient will be assigned.

A baseline measurement of the IIEF-EF and the EHS will be made before starting the intervention; In addition, the AMS questionnaire should be completed to rule out hypogonadism. Once the treatment is completed, patients must complete the IIEF-EF and EHS scales in the last treatment session. In this same session, the patient will be evaluated for adverse events; later, they will have

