a medical follow-up one month after the end of the treatment, in which measurements of effectiveness and safety of the therapy will be made again. If the patient cannot attend the medical follow-up, the surveys will be sent by email on the day of the follow-up appointment and the patient will be contacted by telephone (Figure 2).

Radial wave therapy will be applied with the following parameters: There will be a weekly session of 6 sessions of radial waves. A weekly session of radial waves will be applied with the following parameters: 6000 pulses at 1.5-2.6 bar (depending on patient tolerance), with a frequency of 17Hz, the frequency should increase to 22HZ the first 500 impulses to create mild anesthesia in the area; in all the sessions of radial waves, 4000 impulses will be distributed in the body of the penis in scanning technique and 2000 impulses in the perineal area. The application at the perineal level should be performed with the patient in the supine position in a low lithotomy position, the testicles should be slightly raised to apply the wave on the perineal musculature (ischiocavernosus and bilateral bulbospongiosus).

The placebo therapy will be done with the same machine and the same parameters as the actual therapy, but the adjustment will be made in the handpiece to eliminate the effect of the radial waves.

If there is a difference between placebo therapy and radial wave therapy, patients in the placebo arm will receive the intervention arm scheme, one month after the initial treatment.

All clinical data will be recorded in the electronic medical record of Boston Medical Group and in the database of the study, in the latter a code will be used for the identification of research subjects, thus avoiding the use of the personal patient data. At the end of the collection of the total sample, the missing clinical information will be extracted from the electronic medical record. This information will be exported to a flat file for the corresponding statistical analysis.

The research team will hold meetings every two weeks to monitor the study to validate the data of the base.

Follow-up

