The research subjects will be followed up one month after the end of the treatment. In the event that the patient cannot attend the follow-up, the respective scales will be sent to his e-mail so he can process them and return them by the same means; if after 3 days no response is received, a research assistant will call him and apply the questionnaires by telephone.

Statistical Analysis

A descriptive analysis of the individuals' baseline characteristics linked to each treatment arm will be made, estimating measures of central tendency and dispersion in the case of continuous variables, and measures of relative and absolute frequency for categorical variables.

To evaluate the effectiveness of the therapy, the change in the IIEF-EF scale will be compared at the end of the treatment with the baseline score for each of the arms, using parametric tests in case the

data present a normal distribution, or nonparametric tests otherwise. This same analysis will be done for the scores at the one-month follow-up.

For the EHS scale, the change in at least 1 point will be evaluated, in any of the established measurements. The association between the change in the score and the received treatment will be evaluated estimating the relative risk with its respective confidence interval.

The percentage of patients that decrease or discontinue the use of sildenafil in each group will be estimated, comparing the proportion between the groups at the end of the therapy scheme and the month of follow-up, using the Chi-square test.

The incidence of adverse events for each of the intervention groups will be estimated and the value between them will be compared using the Chi-square test.

In addition to the comparison between groups, stratified analyzes will be performed with multivariate regression models to determine how each intervention adjusted for covariates, such as comorbidities or additional treatments.

An interim analysis will be done once 60% of the total number of patients has completed the treatment (main outcome).

Expected impact

The main contribution of this study is for the scientific community and for patients with erectile dysfunction, by collecting scientific evidence of quality that allows to make a decision about the use of radial waves for the management of erectile dysfunction.

Ethical aspects

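### The plan gives no stated way to collect the primary end-of-treatment IIEF-EF from patients who stop early, although it gives one for the secondary one-month score

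*Combined protocol and SAP*

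**What the plan says.** The Primary Outcome section places the endpoint at the end of treatment: "The primary outcome of this study is the difference in the average score of the IIEF-EF scale (Annex 3) in at least 5 points". The section on techniques, procedures and data collection gives two measurement points up to then. The first is baseline: "A baseline measurement of the IIEF-EF and the EHS will be made before starting the intervention". The second is the end of the course. The sentence opens with the condition that treatment has been completed, and continues: "patients must complete the IIEF-EF and EHS scales in the last treatment session". The course is six weekly sessions.

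The same section then turns to the one-month visit: "If the patient cannot attend the medical follow-up, the surveys will be sent by email on the day of the follow-up appointment". The Follow-up section, which is about that same visit, adds the next step: "if after 3 days no response is received, a research assistant will call him and apply the questionnaires by telephone". Under Secondary outcomes, the IIEF-EF at one month is a secondary outcome.

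The Sample size section allows for loss ("Adjusting for a percentage of losses of 20" per cent), which takes 33 per group to 40. The text describes no assessment at early termination, no IIEF-EF at the sessions in between and no remote route for the end-of-treatment questionnaire. It also names no analysis set and no method for missing scores.

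**The concern.** The one post-baseline score that decides the trial depends on the patient being present at the end of the course. A man who gives up after three sessions, or simply fails to return, has no later occasion on which the plan asks for that score. The less important time point has a three-step rescue (email, three-day wait, telephone) and the primary has none.

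The primary comparison then becomes largely a comparison of completers, and randomisation no longer guarantees that the two sets of completers are alike. If patients leave for reasons tied to how they are doing, and do so differently by arm, the difference in mean change is biased. A questionnaire that was never administered cannot be recovered by later analysis. The EHS at the end of treatment is collected in the same session and has the same gap.

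**Working it through.** **1. The passages side by side.**
- End of treatment (primary): collected in the last session, after treatment is completed. No alternative is given.
- One month (secondary): collected at a visit, otherwise by email, otherwise by telephone.
- The interim-analysis sentence in Statistical Analysis counts patients who have completed treatment and labels this the main outcome. That again ties the primary score to completion.
- The plan to fill gaps from the electronic medical record retrieves only what was already recorded.

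**2. The plan's own loss figure.** 33 x 1.20 = 39.6, rounded to 40 per group. Conversely, 20% of 40 is 8, which leaves 32 against the 33 that the plan requires. The loss is therefore already budgeted, and power is not part of this point. (Whether 33 follows from the stated significance level is a separate question that does not bear on this one.)

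**3. Size of bias, by arithmetic.** In one arm let m be the share missing and g the gap in mean change between completers and stoppers. The all-patient mean is (1 - m) x completers + m x stoppers, so the completer mean exceeds it by m x g. The bias in the between-arm difference is

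m(active) x g(active) - m(sham) x g(sham).

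- Loss in the active arm only, m from 10% to 20%, g from 3 to 8 points (all assumed): 0.10 x 3 = 0.3 up to 0.20 x 8 = 1.6 points.
- Equal m and g in both arms: zero.
- Selective loss in sham only: the same size with the opposite sign.

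**4. Size of bias and error, by simulation.** SD 8 and 40 per arm come from the Sample size section, as does the one-sided 2.5% level (the plan's one-tailed 97.5%, read as alpha 0.025). Assumed: no true effect, and a chance of loss that rises e-fold per SD of poorer change (full strength) or half that on the log scale. A fixed number is lost per arm; 20,000 replicates; completers compared by t-test.

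| Loss active / sham | Selective in | Strength | False gain (points) | One-sided error |
|---|---|---|---|---|
| 20% / 20% | active only | full | 1.51 | 12.5% |
| 30% / 10% | both | full | 1.55 | 13.9% |
| 20% / 20% | active only | half | 0.86 | 6.5% |
| 10% / 10% | active only | full | 0.75 | 6.2% |
| 20% / 10% | both | full | 0.77 | 6.9% |
| 20% / 20% | both | full | about 0 | 3.4% |

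With losses drawn independently (logistic) instead of a fixed count, in a run of 8,000 replicates, the first two rows become 1.40 points and 10.8%, and 1.31 points and 9.7%. The equal case gives 2.7%, so the 3.4% in the last row partly reflects fixing the number lost.

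**5. How strong these assumptions are.** By the formula in step 3, the first row implies a gap of 1.51 / 0.20 = 7.55 points between completers and stoppers, close to one SD (7.55 / 8 = 0.94). The half-strength row implies 0.86 / 0.20 = 4.3 points. The upper figures therefore need strong selection.

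**The case against.** **The wording leaves room.** The text says the last treatment session and does not name session 6. A patient who announces that he is stopping could fill in the scales at the last session he attends. This stands in part, but the opening condition, that treatment is completed, points to the end of the course, and neither reading reaches a man who simply does not come back. Figure 2, which the procedures section cites, was not available in the text reviewed. If it shows an early-termination assessment, the text should say so.

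**Early stoppers are not lost altogether.** A reader might infer that they have no outcome data. The documents do not support that, because nothing bars them from the one-month contact. That contact yields the secondary time point, however, and its date is unclear for someone who stops early because it is counted from the end of treatment.

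**The loss allowance.** A reader might infer that 8 patients per arm will lack the primary score, or that power is lost. The 20% is a general allowance, not a forecast of early stopping, and the sample size already includes it.

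**Differential stopping may be small.** Patient, physician and the person applying the questionnaires are masked, and pressure in the active arm is adjusted to tolerance. Both limit differential stopping. They do not exclude it: the active handpiece delivers the impulses and the sham does not, so tolerability may differ.

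**Direction.** If the therapy works, stopping for lack of benefit would tend to remove poor responders from sham, which biases against the active arm. This stands; the bias is not necessarily in favour of the therapy.

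**As-treated analysis.** A reader might infer from the EHS phrase "the change in the score and the received treatment" that the plan leaves the randomised groups. That over-reads one phrase about a secondary outcome; the rest of Statistical Analysis compares the arms or groups.

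**Conclusion.** The point holds as a gap in data collection. As written, the primary score is sought only from patients who reach the end of the course, while the secondary time point has a remote back-up. The primary comparison would be largely among completers.

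Whether that biases the result is not known from the documents, which give no figures for who stops or why. Across the unequal scenarios assumed above (selective loss, 10-30% per arm, SD 8, 40 per arm, no true effect) the false difference is about 0.75-1.5 points. Against the 5-point target that is 0.75 / 5 = 15% to 1.5 / 5 = 30%. The error of about 6-14% instead of 2.5% applies when the bias favours the active arm. With equal loss and selection the bias is about zero; with selection mainly in sham the sign reverses. The collection gap rests on the text and is well supported. The size of the bias is illustrative only. The change should be made, because the omission cannot be repaired after the data are in and the remedy is cheap.

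**What to change.** In the procedures section, require the IIEF-EF and EHS from every randomised patient at the scheduled date of session 6, whether or not the sessions were completed. For those not present, use the email, three-day wait and telephone steps already written for the one-month visit. In Statistical Analysis, state that all randomised patients are analysed in the arm assigned, and say how scores still missing are handled. A repeated-measures model that also uses the one-month score is an option but not required. It would not in general remove bias when loss depends on the unobserved change itself, so collecting the score matters more than the choice of model.

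The cost is a few sentences and a small number of contacts: at most about 2 x 8 = 16 patients if the whole 20% allowance were early stopping. The downside is that a few primary scores would be completed by email or taken by telephone, a mode that the plan already accepts at one month. No treatment changes.

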 impulses in the perineal area.
- Arm 2 (Standard treatment (oral sildenafil) + Placebo therapy): Sildenafil according to the patient's degree of affectation + 6 sessions of placebo therapy. There will be a weekly session of placebo wave therapy, using the respective device to prevent the patient from receiving the radial wave. The same parameters of the "real" therapy will be used: 6000 pulses at 2.6 bar, with a frequency of 17 Hz; in all radial wave sessions, 4000 impulses will be distributed in the body of the penis in scanning technique and 2000 impulses in the perineal area.

Measurements will be made of the EHS and IIEF-EF scale scores, of the use of medication and of the possible adverse events of the therapy, at the beginning and end of the treatment, and one month after the therapies are finished.

Expected impact: Knowing the effectiveness and safety of radial waves for the treatment of erectile dysfunction will allow having a scientific basis for new treatment alternatives for men with this disease.

Introduction

Erectile dysfunction (ED) is defined as the persistent inability to reach and / or maintain an erection sufficient to allow a satisfactory sexual relationship (1). Epidemiological information on ED shows that it is a condition that has a high prevalence and incidence worldwide and that mainly affects men over 40 years of age (2). The prevalence of ED in the general population of men under 40 years of age is approximately between 1% and 10% (3). Both prevalence and severity increase with age, in men between 60 and 69 years of age, the prevalence of erectile dysfunction increases from 20% to 40%, and this range can increase from 50% to 100% in men between 70 and 80 years old (3-6).

Currently, there are different pharmacological and non-pharmacological treatments for erectile dysfunction, among which are the administration of medicines for oral use, intracavernous and intraurethral, lifestyle modification, vacuum devices, psychotherapy, extracorporeal therapy with low intensity shock waves (Li-ESWT), vascular surgery for selected cases, and alternative therapies (7-14).

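### Adverse event assessment times differ between the Abstract, the Safety section and the procedures, and no passage covers patients who stop early, so events in sessions 1 to 5 may be under-recorded

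*Combined protocol and SAP*

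**What the plan says.** Three places in the combined protocol and SAP set the timing.

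- **Safety:** "These will be evaluated at the end of each of the therapies and a month of follow-up".
- **Techniques, procedures, data collection and processing** (the procedures section): at the end of treatment, "patients must complete the IIEF-EF and EHS scales in the last treatment session", and then "In this same session, the patient will be evaluated for adverse events". The one-month visit follows, "in which measurements of effectiveness and safety of the therapy will be made again". No adverse event assessment is mentioned for sessions 1 to 5.
- **Abstract:** the measurements include "possible adverse events of the therapy, at the beginning and end of the treatment, and one month after the therapies are finished".

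Treatment is six sessions, one a week. The Safety section fixes the form of the outcome: "This variable will be dichotomous as the presence or absence of adverse events". Type and severity are also recorded. Comparing adverse event incidence between arms is secondary objective 4, and the Statistical Analysis section tests it with a Chi-square test.

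If the one-month visit is missed, the procedures and Follow-up sections provide for email and then telephone contact. They describe what is sent or administered as surveys, scales or questionnaires. Adverse events are not named.

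**The concern.** A yes/no outcome of any event per patient is sensitive to how often the patient is asked. A patient with a brief local reaction after session 2 counts as having an event if asked that day. If first asked at session 6, four weeks later, he counts only if he remembers and reports it. Two clinics, in Bogotá and Lima, could in good faith follow different timetables, and their rates would not then be comparable.

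The second gap concerns patients who stop early. The procedures tie the on-treatment assessment to the last treatment session, and no passage says how events are collected from a patient who does not complete the course.

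Safety is in the trial's title and objective, and the Ethical aspects section classes the study as carrying more than minimal risk. The completeness of this outcome therefore deserves a clear rule.

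**Working it through.** **Step 1: the texts side by side.**

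| Time point | Safety | Procedures | Abstract |
|---|---|---|---|
| Beginning | not named | not named for adverse events (baseline is IIEF-EF, EHS and AMS) | yes |
| Sessions 1 to 5 | yes, on the natural reading | not named | not named beyond the beginning |
| Last session / end of treatment | yes | yes | yes |
| One month | yes | yes | yes |
| Patient who stops early | no rule | no rule | no rule |

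The Safety wording could mean the end of each arm's course instead of each session. That is less natural: the Abstract uses the plural for the sessions being finished, and the Statistical Analysis section calls the whole course a scheme. If the other reading were intended, Safety and procedures would agree, but no text would then require an assessment after each of sessions 1 to 5.

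**Step 2: how much could be lost.** The documents give no adverse event rate. The Ethical aspects section says only that reported rates are very low. There is thus no plan figure to reproduce, and what follows is an illustration.

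Inputs:
- number of sessions: 6 (from the plan);
- p, the chance of an event at each session, taken as equal and independent across sessions: assumed;
- r, the fraction of events from sessions 1 to 5 that is recovered at the last session: assumed.

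The one-month visit is taken to recover nothing further from the treatment period.

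Formulas:
- true incidence over the course = 1 − (1 − p)^6
- recorded by one assessment at the last session = 1 − (1 − p)(1 − p·r)^5

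For p = 0.02:
- true: 1 − 0.98^6 = 11.4%
- r = 0: 1 − 0.98 = 2.0%
- r = 0.5: 1 − 0.98 × 0.99^5 = 6.8%
- r = 0.8: 1 − 0.98 × 0.984^5 = 9.6%
- r = 1: 1 − 0.98^6 = 11.4%

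| p per session | True | r = 0 | r = 0.5 | r = 0.8 | r = 1 |
|---|---|---|---|---|---|
| 2% | 11.4% | 2.0% | 6.8% | 9.6% | 11.4% |
| 5% | 26.5% | 5.0% | 16.3% | 22.5% | 26.5% |
| 10% | 46.9% | 10.0% | 30.4% | 40.7% | 46.9% |

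With the planned 40 per arm and p = 2%, 40 × 11.4% = 4.6 patients have an event. The number recorded would be 0.8 (40 × 2.0%), 2.7 (40 × 6.8%), 3.8 (40 × 9.6%) or all 4.6.

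**Step 3: effect on the comparison.** Suppose p is 5% in one arm and 2% in the other, with equal recall.

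| Capture | Incidence | Difference | Ratio |
|---|---|---|---|
| Every session, or r = 1 | 26.5% vs 11.4% | 15.1 points | 2.3 |
| Last session, r = 0.5 | 16.3% vs 6.8% | 9.5 points | 2.4 |
| Last session, r = 0 | 5.0% vs 2.0% | 3.0 points | 2.5 |

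The absolute difference shrinks, and power with it. The relative risk does not move towards 1.

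**Step 4: early stoppers.** The Sample size section allows for 20% losses, which is 0.20 × 40 = 8 per arm. Losses are not split into patients who stop treatment and patients lost after finishing it, so 8 is only an upper bound on the planned-for patients without a last-session assessment.

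**The case against.** The strongest reply is that the timetable needed is already in the plan. The Safety section defines this outcome and, on its natural reading, requires assessment after every session. The procedures sentence describes the end-of-treatment visit and does not say that it is the only assessment, and the Abstract is a summary. Nothing in the documents says that sites work from the procedures alone. This shows that the texts can be reconciled, but not that they agree. A reader of the procedures or the Abstract is not told to ask after each session.

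A reader might infer that following the procedures is bound to miss events in sessions 1 to 5. The documents do not support that. The last-session evaluation has no stated look-back limit, so earlier events may be reported then. The procedures section also has clinical data entered in the electronic medical record and missing items extracted from it, and safety is measured again at one month. This part of the objection stands, and possible under-recording is as far as the text goes. Equally, no passage asks for a look-back or requires anyone to ask and record at each session.

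On early stoppers, the last treatment session could mean the patient's own last session, and he might be reached at one month. That is fair: the documents show a missing rule, not a certain loss.

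**Conclusion.** The concern holds as an inconsistency in a secondary outcome, together with a missing rule for early stoppers. If sites follow the procedures or the Abstract, the recorded incidence may be too low. At an assumed 2% per session it lies anywhere from 2.0% to the full 11.4%, depending on recall. The range rests on equal, independent session risks and on nothing being recovered from the medical record or at one month.

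Two stronger conclusions are not supported. One is that the safety comparison is biased towards no difference. With equal recall the absolute difference and power fall, but the relative risk need not move towards 1. A differential loss would require events to cause stopping more often in one arm, and the documents give no evidence on that. The other is that 8 patients per arm would go unassessed, since that figure is an upper bound on losses of every kind.

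This is a cheap improvement worth making. It is not a flaw that invalidates the safety analysis.

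**What to change.** - Make the Abstract and the procedures section match the Safety section, and word the Safety section so that it plainly means each session. Adverse events since the last visit are then asked about at each of the six weekly sessions and at one month.
- Add adverse events to what the email and telephone route collects, and use that route for patients who stop treatment early.
- State that a patient counts as having an event if one is recorded at any of these times.

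The cost is wording, one short question at visits that already take place, and a few extra calls. Compared with the procedures as written, five sessions gain the question, at most 5 × 80 = 400 askings over the trial.
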